## **5.6.D Data Analysis Logistics**

Phase 2: VA administrative data will be accessed and stored on the VA's centralized and secure Information and Computing Infrastructure (VINCI). VINCI is a major informatics initiative of the Department of Veterans Affairs (VA) that provides a secure, central analytic platform for performing research and supporting clinical operations activities. It is a partnership between the VA Office of Information Technology (OI&T) and the Veterans Health Administration Office of Research and Development (VHA ORD). VINCI includes a cluster of servers for securely hosting suites of databases integrated from select national VA data sources. VINCI servers for data, applications, and virtual sessions are physically located at the VA Austin Information Technology Center (AITC), located in Austin, Texas. This secure data storage enclave has multiple layers of security and disaster recovery to prevent data loss. To ensure the protection of Veteran data, VINCI maintains compliance with the guidelines set forth by Veterans Health Administration (VHA) Handbook 1200.12. Accesses to VINCI resources are approved in accordance with the requirements of National Data Systems (NDS), "VHA Handbook 1200.12, Use of Data and Data Repositories in VHA Research", and all other applicable VA and VHA policies and regulations. Study data stored on VINCI servers are located at the Austin Information Technology Center, [name].

Data necessary for recruitment will be imported into a study database stored on the local drive. Recent experience has shown that, at the moment on the VINCI platform, access and computing is very slow compared to the local servers. Storing the database locally will provide broader, faster access to research staff who are delegated to use the database. Accordingly, we will house the MS Access database for recruitment and data collection on the local server. As MS Access is not feasible to use on VINCI, research staff will prepare a limited data set which meets HIPAA standards which can then be downloaded via secure FTP from VINCI to a local VA secure server located at the Houston VA HSR&D IQuEST. This limited data set will then be imported to the MS Access database stored on the Houston VA HSR&D IQuEST secure server. Preparation of the limited data set to be downloaded to the Houston VA IQuEST shared drive will occur only within the VINCI secure platform. Copies of other data sources will be uploaded to the Project folder within VINCI from the location of current storage after appropriate approvals with the data custodians are established.

Data analyses will take place with a number of statistical programs including SAS, and potentially Microsoft SQL Server (T-SQL), Stata, and/or R. All these resources are available to research staff on the VINCI secure computing platform, reducing the need for large data transfers to local VA secure servers. However, one resource that is lacking at the moment on the VINCI platform is the software which will be used to statistically analyze the constructed cohort files. Mplus is a versatile and commonly used structural equation modeling software application which has been approved and tested by VA OI&T for use within the VA. This software will be used to complete the final inferential statistical analyses in this protocol. Current software applications on the VINCI system (e.g., SAS, Stata, R) do not yet contain procedures/packages which can accommodate the inferential statistical analyses outlined in this protocol. As Mplus is not available on VINCI yet, research staff will prepare a limited data set which meets HIPAA standards which can then be downloaded via secure FTP from VINCI to a local VA secure server located at the Houston VA HSR&D IQuEST. This limited data set will then be analyzed from the Houston VA HSR&D IQuEST secure server. Preparation of the limited data set to be downloaded to the Houston VA IQuEST shared drive will occur only within the VINCI secure platform. Analyses with VA data that do not involve the structural equation models described in this protocol will be completed in the VINCI workspace and secure computing resources provided by VINCI staff (e.g., SAS, MS SQL Server, Stata, or R). However, once the cohort files have been constructed and are suitable for structural

equation modeling, preparation of the limited data set will then involve removing all patient identifiers. For this protocol, patient identifiers include the VA's scrambled SSN (SCRSSN), real SSN, dates, and zip codes. The limited data set will then be stripped of these patient identifiers in the following process before transfer from the VA's VINCI platform to the Houston IQuEST local secure server:

- 1) Real SSN will be completely deleted immediately from the limited data set.
- 2) PatientSID and PatientICN variables from CDW will be completely deleted from the limited dataset,
- 3) SCRSSN will first be sorted randomly in the dataset and then encoded to anonymous numbering (i.e., 1, 2, 3, 4...N) unique to this limited data set. This procedure anonymizes the records with respect to individual VA patient identification, but preserves the essential nesting structure of multiple non-independent records nested within participant in the limited dataset. SCRSSN will then be completely removed from the limited data set prior to download from VINCI FTP to the local Houston VA IQuEST secure server.
- 4) Similar to SCRSSN, dates will be encoded such that the same dates in the limited data set retain the same ordering, but values will not be identified as dates. For example, SEP272013 might be coded as 74 with SEP282013 coded as a 75, and so on. This approach preserves the order and parametric qualities of former date variables, but does not allow any identification of actual dates of care in the limited data set. Actual date values in the entire limited data set will then be deleted prior to download from VINCI FTP to the local Houston VA IQuEST secure server.
- 5) As with the process of anonymizing SCRSSN and deleting this variable, zip codes will be encoded such that the zip code variable will first be sorted randomly and then encoded to non-identifying numbers unique to this limited dataset. For example, zip code 55555 might be coded as 1, 72468 might be coded as 2, 56912 might be coded as 3, etcetera. This step will again be completed in VINCI prior to secure FTP download to the Houston VA IQuEST's secure server. After encoding zip code, zip code will be deleted from the limited dataset.
- 6) Final checks that all identifying information has been removed from the dataset will be made, and
- 7) The limited data set will be transferred from VINCI to Houston VA's IQuEST secure server for analysis with VA approved Mplus software (once again, as this software is not available on the VINCI platform, but approved by VA OI&T).
- 8) No means of linking VA data stored in the VINCI project workspace with values in the limited data set will be available outside of VINCI.

It is important to note that VINCI has an audit function built in such that review of FTP downloaded data does not violate HIPAA or VA policies. The 8 step approach outlined above, along with this audit/data download monitoring function that VINCI maintains will ensure that PII/PHI remain securely protected and confidential.

The primary person(s) processing and analyzing data will be the Houston Data Analyst(s). The Houston-based investigators ([name], [name], [name], [name], and [name]) will assist with data analysis when needed. [name] will have primary responsibility for oversight of all data analysis work.

## **5.7 Withdrawal of Subjects**

### **5.7.A. Group Leaders and Individual Session Providers.**

**5.7.A.i. Investigator termination of subject participation:** The investigator does not anticipate any circumstances under which subjects will be withdrawn from the research without their consent.

**5.7.A.ii. Consequences of withdrawal:** If a participant decides to withdraw, there are no foreseeable consequences. A replacement will need to be identified, consented and trained to complete study enrollment.

**5.7.A.iii. Procedure for orderly termination of participation by the subject:** The subject must notify the investigator, or Research Coordinator, by telephone or written correspondence of their desire to withdraw from the study. When possible, the subject will finish working with the current cohort of subjects before terminating participation.

## **5.7.B. Patient Participants**

**5.7.B.i. Investigator termination of subject participation:** The investigator does not anticipate any circumstances under which subjects will be withdrawn from the research without their consent unless the participant develops a condition on the exclusion criteria that will put them at risk.

**5.7.B.ii. Consequences of withdrawal:** If a participant decides to withdraw prior to the completion of the baseline assessment, the only consequence to the subject would be not receiving study compensation (because they would not have completed baseline assessment as required). If a participant decides to withdraw at any point after baseline, there are no foreseeable consequences.

**5.7.B.iii. Procedure for orderly termination of participation by the subject:** The subject must notify the investigator, or Research Coordinator, by telephone or written correspondence of their desire to withdraw from the study.

## **6.0 Reporting**

All unanticipated serious adverse events (U-SAEs) and unanticipated serious problems (UAPs) will be reported to the VA Central IRB within five business days. U-SAEs will be reported to VA Central IRB regardless of their relationship to the research. All protocol deviations, violations, and/or noncompliance will be reported to the VA Central IRB within five business days of the reporting individual becoming aware of the occurrence.

### Safety information, including SAEs, that will be collected:

Occurrences of events resulting in a participants' death, life threatening experience, hospitalization, prolonged hospitalization, or persistent or significant disability related to hypoglycemia will be defined as a Serious Adverse Event and documented. Any occurrence of

an event that results in the need for medical or other interventions to prevent any of the above listed outcomes will be documented as well. As such, any participants identified as having an immediate physical health issue will be referred to care as appropriate.

Frequency/methods of safety-related data collection:

Collection of safety information will commence when the first participant is enrolled in the study; this is anticipated to occur during Spring 2015. Safety information may be collected either 1) during baseline and follow up assessments, 2) during EPIC sessions, or 3) during telephone contacts with participants made for purposes of scheduling assessments and/or treatment sessions. Also, the Research Coordinator or RA will periodically contact patients to schedule study-related safety appointments. The participants or other informants may report information related to their safety at those times.

Conditions that would trigger an immediate suspension of the research:

This intervention will compare a brief, structured goal-setting intervention with usual care practices in VA facilities. The active treatment (EPIC) utilizes an empirically-supported theory to enhance patients' self-management of diabetes. No invasive procedures or untested techniques will be used. As such, this protocol is judged to be of low risk. We do not anticipate the occurrence of events that would necessitate the immediate suspension of research because of 1) the low probability of adverse events from the intervention in either arm of the study, 2) all participants will continue to receive usual care services within the VA, and 3) treatment for any VA services will not be withheld from any participants.

Specify procedures to determine when and how to notify individual participants or their health care providers of findings that may affect the participant's health or welfare:

The decision to contact a patient and/or their health care provider regarding patient welfare can be made in two ways. First, the Project Coordinator or research staff will conduct routine checks on participants' safety and well-being during baseline and follow up assessments. The study personnel will notify the patient and/or their healthcare provider as necessary.

Second, data and safety monitoring is expected to be conducted at both the local and national levels. At the local level, the study PI ([name]), site PIs ([name], [name], [name]), co-investigators ([name], [name], [name], [name]) will work with the study programmer and statistician to review data and safety issues regularly during monthly investigator meetings or more immediately as needed. Data and safety monitoring will occur for any identified adverse events as well as including a regular monitoring schedule of participant longitudinal data. Any participants identified as having an immediate physical health issue will be referred to care as appropriate. All participants, regardless of treatment, with a 20% increase in symptoms (relative to baseline) will be called to ensure safety and encourage the participant to obtain care if desired.

At the national level, we anticipate participating in the VA's Data and Safety Monitoring Board (DSMB). We will provide the national DSMB with comprehensive annual and semi-annual reports, as directed, for formal independent review of study safety and recruitment practices.

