To personalize goal-setting and action planning around levels of health literacy (see Table 8), participants will learn widely advocated interactive communication strategies for patients with low literacy levels. Strategies will include the use of “conversational language” (e.g., “sugar” for glucose) and simple techniques such as making eye contact to promote patient understanding. Participants will also learn and practice the “teach back” technique to verify patients’ understanding of the information discussed in the one-on-one sessions. They will be instructed to assess and re-assess understanding until the patient demonstrates comprehension by correctly repeating the content back to the PACT member each time a new topic is introduced or a new goal is set. Using “teach back” has been shown to improve glycemic control among diabetes patients with low literacy levels. To personalize goal-setting based on literacy, participants will learn how to simplify specific goals (e.g., using the plate method vs. reading food labels) within a general category (e.g., diet) for patients with limited FHL (Table 8).

**5.1.F.iii. Fidelity measures.** We will use three strategies to assess fidelity to the conduct of the EPIC intervention. We used these strategies in our previous trials to ensure that the intervention is conducted as intended:

1) Number of treatment sessions: We will track the number of treatment sessions that each patient-participant actually receives compared to the prescribed number of sessions (i.e., six group sessions and six one-on-one sessions). This is the only measure that will be applied to both individual and group sessions.

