#### **5.1.K. Protection Against Risk**

To ensure protection against potential risks, Phase 1 was approved by the Baylor College of Medicine Institutional Review Board and the Michael E. DeBakey VA Medical Center Research and Development Committee. The protocol for Phase 2 will be approved by, the VA Central IRB. In addition, we will obtain approval from the appropriate local VISN 12 and Houston-based VA R&D committees.

The following precautions will be taken with both staff and patient-participants to address possible apprehension with disclosing health care related information. Study participants will be assured that:

- Participation is voluntary;
- They do not have to answer any questions with which they are uncomfortable;
- They can discontinue study participation at any time; and
- Participation will in no way affect the care that patients receive at the VA or employment status for VISN12 or Houston staff members.

In addition, the following precautions will be taken to minimize the risk of loss of confidentiality for all participants in the study:

- All paper patient data will be coded by study ID without identifying information, and any personal identifiable data will be stored separately behind two locks in a cabinet within the PI's office. Access to these files will be restricted to study personnel.
- All electronic data will be maintained on IQuEST's secure and fully backed up UNIX data server, with appropriate ID, password, and data access restrictions.
- All study results and accompanying publications will be anonymous, and will not contain identifiable information.

Some patients may experience clinically significant symptoms of hyper or hypoglycemia during the course of the intervention. We will have protocols for addressing this risk by:

- a) First alerting study PIs and then participants' PACT provider when symptoms are more than minor,
- b) Assisting participants to develop communication action plans with clinicians when symptoms are mild but warrant discussion with clinicians, and the
- c) Reporting significant adverse events to the Institutional Review Board (IRB) when emergent care is required.

Each step will have a protocol specific to each facility's workflows and regulation, and we will then train local study staff, group leaders and individual session providers on the implementation of the protocols accordingly.

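### Safety events are looked for more often in EPIC than in EUC, and, separately, the SAE definition is not reconciled with the protocol's other safety-reporting rules

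*Combined protocol and SAP*

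**What the plan says.** **Sources of safety information.** Section 6.0, under the heading on safety information to be collected, states: "Safety information may be collected either 1) during baseline and follow up assessments, 2) during EPIC sessions, or 3) during telephone contacts with participants". The calls in the third item are those made to schedule assessments, treatment sessions or both. The same paragraph adds that "the Research Coordinator or RA will periodically contact patients to schedule study-related safety appointments". Later in 6.0, staff are to "conduct routine checks on participants' safety and well-being during baseline and follow up assessments", and any participant in either arm whose symptoms rise 20% over baseline is to be called.

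**Contacts by arm.** Section 5.1.F.iii sets the EPIC prescription at "six group sessions and six one-on-one sessions". Sections 5.1.A and 5.1.E.iv give EUC patients a nurse referral, an educational packet and a letter, with no study sessions. Both arms are assessed at baseline, at about 4 months and at 10 months.

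**SAE definition.** Section 6.0 lists death, life-threatening experience and further outcomes, ending: "hospitalization, prolonged hospitalization, or persistent or significant disability related to hypoglycemia will be defined as a Serious Adverse Event". Section 5.1.N uses the label SAE for hospitalizations tied to a hypoglycemic event and lists them in addition to unanticipated SAEs (U-SAEs).

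**Other reporting rules.** Sections 5.1.N and 6.0 both say that "U-SAEs will be reported to VA Central IRB regardless of their relationship to the research". Section 5.1.K warns: "Some patients may experience clinically significant symptoms of hyper or hypoglycemia during the course of the intervention". It then calls for significant adverse events to go to the IRB when emergent care is needed.

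**The concern.** There are two separate issues.

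**Unequal observation.** If one arm has more occasions on which an event can come to light, its recorded count can be higher with no difference in true risk. Hypoglycemia is the risk of the intervention that 5.1.J itself names, so it is where an imbalance between arms would be examined first. Adverse events go to the quarterly monitoring meetings (5.1.N) and to the national monitoring board (6.0), and would be expected in the final report.

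**SAE wording.** If an event counts as an SAE only when it is related to hypoglycemia, then an admission for hyperglycemia, or a death from another cause, is not an SAE. It then cannot be a U-SAE either, and the rule to report U-SAEs whatever their relationship to the research loses most of its scope. Sites could reasonably differ on which events to document as serious.

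**Working it through.** **1. Scheduled contacts after randomization**

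The plan gives no figure of its own to reproduce here. Baseline is left out because consent, the baseline surveys and the baseline HbA1c all precede randomization (5.2.B.i, steps 5 to 7).

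| | EPIC | EUC |
|---|---|---|
| Follow-up assessments (5.1.A) | 2 | 2 |
| Group sessions (5.1.F.iii) | up to 6 | 0 |
| One-on-one sessions (5.1.F.iii) | up to 6 | 0 |
| Total | up to 14 | 2 |

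- Ratio: 14 / 2 = 7.
- Section 5.1.E.iii allows a one-on-one to be held straight after its group session. If each pair counts as one contact, EPIC has 6 + 2 = 8, and the ratio is 8 / 2 = 4.
- Not counted, because no number is stated: calls to schedule assessments, symptom-triggered calls and periodic safety contacts (both arms), and calls to schedule treatment sessions (EPIC only).
- The routine checks in 6.0 take place at the assessments, so they are already in the table.
- The measures table (Table 10) lists no safety instrument.

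**2. What unequal detection could do (illustration)**

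The documents give no event rate and no detection rate. The following are assumptions: equal true risk p in both arms; 90% of events detected in EPIC; 75%, 60% or 45% detected in EUC. The 142 patients per arm come from 5.6.A.

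- Apparent risk ratio = (p × 0.90) / (p × EUC detection): 0.90/0.75 = 1.2, 0.90/0.60 = 1.5, 0.90/0.45 = 2.0.
- Expected recorded events at p = 10%: EPIC 142 × 0.10 × 0.90 = 12.8. EUC: 142 × 0.10 × 0.75 = 10.7, × 0.60 = 8.5, × 0.45 = 6.4.
- Chance that a two-sided 5% test of two proportions (normal approximation) shows an excess in EPIC, where equal detection would give 2.5%:

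| True risk | EUC 75% | EUC 60% | EUC 45% |
|---|---|---|---|
| 5% | 5% | 10% | 18% |
| 10% | 7% | 16% | 33% |
| 20% | 10% | 29% | 60% |

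The approximation is rough at counts this small. The table shows direction and order of size only.

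**3. The SAE texts side by side**

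- *Section 6.0, definition.* The phrase on hypoglycemia closes the list. It can govern the whole list or only its last item, disability.
- *Section 5.1.N, label.* Using SAE for hypoglycemia-related hospitalizations favours the narrow reading.
- *Section 5.1.N, structure.* Listing those hospitalizations in addition to U-SAEs implies that U-SAEs reach beyond hypoglycemia, which favours the wide reading.
- *Section 5.1.K.* It covers hyperglycemia as well and uses a third standard, a significant adverse event needing emergent care.

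No single definition fits all four comfortably.

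**The case against.** **On observation.** Several channels reach both arms, and the protocol says only that safety information may be collected at sessions; it describes no structured questioning there. The contact count measures opportunity, not detection. All of this stands, and it is why the conclusion is that counts could differ, not that they would. It does not remove the asymmetry, because the shared channels have no stated frequency or script and nothing scheduled in EUC offsets the sessions. A reader might infer that EPIC counts would be inflated. Fuller capture in EPIC may equally be described as under-ascertainment in EUC, and the documents do not support the stronger wording.

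**On consequences.** A reader might also infer that safety could not be compared at all. Section 5.6 plans no between-arm safety test, 6.0 sets no event-based trigger for suspension, and the hypotheses on HbA1c and distress do not depend on adverse-event counts. What is affected is safety monitoring and any adverse-event table by arm.

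**On the definition.** It is tempting to say that the SAE definition contradicts the U-SAE rule. Relation to hypoglycemia and relation to the research are different attributes, so both rules can be applied literally, and the key sentence is grammatically ambiguous. Nor are events outside the SAE label necessarily lost. Section 5.1.K reports events needing emergent care, 5.1.N brings adverse events of any kind to the quarterly meetings, and 6.0 covers unanticipated serious problems and monitoring of identified adverse events. The supportable statement is that these texts are not reconciled.

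**Conclusion.** Both points hold, and they are independent: the SAE definition applies equally to both arms and does not cause the unequal observation.

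1. **Safety capture is unequal by arm.** After randomization there are up to 14 scheduled contacts in EPIC against 2 in EUC, or 8 against 2 if one-on-ones directly follow group sessions. These are maxima that assume full attendance, and they exclude contacts whose number is not stated. EUC is less observed, not unobserved. How far this shifts event counts cannot be derived from the documents; the risk ratios of 1.2 to 2.0 above rest wholly on assumed detection rates.
2. **The SAE definition is probably limited to hypoglycemia-related events.** It is not reconciled with the U-SAE rule in 5.1.N and 6.0, or with the hyperglycemia risk and emergent-care reporting in 5.1.K.

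The efficacy conclusions are unaffected. The change is worth making because it is cheap and because hypoglycemia is the outcome on which an artefact between arms would mislead most.

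**What to change.** **Observation**

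- At each existing assessment, ask the same structured questions in both arms on hypoglycemia, hyperglycemia and hospitalization. Section 5.1.H already assigns these assessments to blinded staff.
- Add events from the utilization data that 5.5.A.i already retrieves for the cost analysis in both arms.
- Base any safety summary by arm on these common sources only.
- Keep recording and acting on events learned at EPIC sessions, so that individual protection is unchanged, but list those known only from that source separately.

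**Definition**

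- Reconcile 5.1.K, 5.1.N and the two parts of 6.0 into one SAE definition used throughout. The sponsor should decide its content.
- Record relatedness (to hypoglycemia and to the research) as separate items for each event.

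**Cost.** A wording amendment and a few questions in assessments that already take place. The real work is extracting and classifying utilization records for a purpose other than cost, and there will be more events to document.
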